### 5.2.5 Guidelines for Prolonged QTc

Guidelines for dose modification and stopping criteria due to QTc-prolongation are provided in

**Table 5.9 Withholding and Stopping Criteria for QTc-Prolongation**

| QTc-Prolongation a   | Action and Dose Modification   |
|---|--|
| QTcB ≥501 msec or
uncorrected QT>600 msec or
QTcB>530 msec for subjects with
bundle branch block | Interrupt study treatment until QTcB prolongation resolves to Grade 1 or baseline 
 
• Test serum potassium, calcium, phosphorus and magnesium. If abnormal, correct per routine clinical practice to within normal limits.
 
 Review concomitant medication usage for a prolonged QTc.
Restart at current dose level b
If event recurs, permanently discontinue study treatment |

Abbreviations: msec = milliseconds; QTcB = QT interval on electrocardiogram corrected using the Bazett's formula

- a. Based on average QTc value of triplicate ECGs. For example, if an ECG demonstrates a prolonged QT interval, obtain two or more ECGs over a brief period, and then use the averaged QTc values of the three ECGs to determine if study treatments should be interrupted or discontinued.
- b. If the QTc prolongation resolves to Grade 1 or baseline, the subject may resume study treatment if the investigator and Novartis medical monitor agree that the subject will benefit from further treatment.

### 5.2.6 Guidelines for Pneumonitis

Pneumonitis has been observed in subjects receiving trametinib. To reduce the risk of pneumonitis, subjects will be monitored closely for symptoms, evaluated with imaging and functional tests. Dose modification and supportive care guidelines for pneumonitis are described in Table 5.10.

**Table 5.10 Management and Dose Modification Guidelines for Pneumonitis**

| CTCAE Grade | Adverse Event Management  | Action and Dose Modification   |
|-------------|---|--|
| Grade 1     | 
 
• CT scan (high-resolution with lung windows) recommended
 
• Clinical evaluation and laboratory work-up for infection
 
• Monitoring of oxygenation via pulse-oximetry recommended
 
• Consultation of pulmonologist recommended
 
  | 
 
• Continue trametinib at current dose
 
  |
| Grade 2     | 
 
• CT scan (high-resolution with lung windows)
 
• Clinical evaluation and laboratory work-up for infection
 
• Consult pulmonologist
 
• Pulmonary function tests –if < normal, repeat every 8 weeks until ≥ normal
 
• Bronchoscopy with biopsy and/or BAL recommended
 
• Symptomatic therapy including corticosteroids if clinically indicated
 
 | 
 
• Interrupt trametinib until recovery to grade ≤1
 
• Restart with trametinib reduced by one dose level
 
• Escalation to previous dose level after 4 weeks and consultation with medical monitor possible
 
• If no recovery to grade ≤1 within 4 weeks, permanently discontinue study treatment
 
 |
| Grade 3     | 
 
• CT scan (high-resolution with lung windows)
 
• Clinical evaluation and laboratory work-up for infection
 
• Consult pulmonologist
 
• Pulmonary function tests-if < normal, repeat every 8 weeks until ≥ normal
 
• Bronchoscopy with biopsy and/or BAL if possible
 
• Symptomatic therapy including corticosteroids as clinically indicated
 
  | 
 
• Interrupt trametinib until recovery to grade ≤1
 
• After consultation with medical monitor, study treatment may be restarted reduced by one dose level
 
• If no recovery to grade ≤1 within 4 weeks, permanently discontinue study treatment
 
   |
| Grade 4     | 
 
• Same as grade 3
 
   | 
 
• Permanently discontinue trametinib
 
   |

### 5.2.7 Guidelines for Visual Changes or Specified Ophthalmic Examination Findings

Episodes of visual changes have been observed in subjects receiving trametinib, and ocular adverse events are known to be related to trametinib. An ophthalmologist should be consulted if changes in vision develop. However, if the visual changes are clearly unrelated to study treatment (e.g., allergic conjunctivitis), then monitor closely as it may be reasonable to defer ophthalmic examination. Special attention should be given to retinal findings (e.g., retinal pigment epithelial detachment (RPED) or retinovascular abnormalities (i.e., branch or central retinal vein occlusions (RVO)).

Guidelines regarding management and dose reduction for visual changes and/or ophthalmic examination findings considered to be related to study treatment are provided in Table 5.11.

**Table 5.11 Management and Dose Modification Guidelines for Visual Changes and/or Ophthalmic Examination Findings**

| CTCAE Grade a | Adverse Event Management  | Action and Dose Modification  |
|--------------------------|---|---|
| Grade 1 b     | 
 
• Consult ophthalmologist within 7 days of onset
 
                      | 
 
• If dilated fundus examination cannot be performed within 7 days of onset, interrupt trametinib until RPED and RVO can be excluded by retina specialist/ophthalmologist.
 
• If RPED and RVO excluded, continue (or restart) trametinib at same dose level
 
• If RPED suspected or diagnosed: see RPED dose modification table Y below; report as SAE.
 
• If RVO diagnosed: Permanently discontinue trametinib and report as SAE.
 
 |
| Grade 2 and Grade 3      | 
 
• Consult ophthalmologist immediately
 
• Interrupt trametinib
 
 | 
 
• If RPED and RVO excluded, restart trametinib at same dose level
 
• If RPED diagnosed, see RPED dose modification table below; report as SAE.
 
• If RVO diagnosed: Permanently discontinue trametinib and report as SAE
 
  |

|         |  |   |
|---------|--|---|
| Grade 4 | 
 
• Consult ophthalmologist immediately
 
• Interrupt trametinib
 
• Report as SAE
 
 | 
 
• If RPED and RVO excluded, may consider restarting trametinib at same or reduced dose after discussion with study medical monitor
 
• If RVO or RPED diagnosed, permanently discontinue trametinib
 
 |
|---------|--|---|

Abbreviations: RPED = retinal pigment epithelial detachment; CTCAE = Common Terminology Criteria for Adverse Events; RVO= retinal vein occlusion; SAE = serious adverse event

- a. Refers to CTCAE Version 4.03 'Eye disorders – Other, specify'
- c. If visual changes are clearly unrelated to study treatment (e.g., allergic conjunctivitis), monitor closely but ophthalmic examination is not required.

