**Table 5.3 Dose Delay and Modification for Events Considered Related to Trametinib**

| CTCAE Grade | Action and Dose Modification  |
|-------------|---|
| Grade 1     | 
 
Continue trametinib at current dose level
 
Monitor closely
 
Provide supportive care according to institutional standards
 
  |
| Grade 2     | 
 
Interrupt trametinib if clinically indicated
 
Monitor closely
 
Provide supportive care according to institutional standards
 
When toxicity resolves to Grade 1 or baseline, restart trametinib at current dose level
 
  |
| Grade 3     | 
 
Interrupt trametinib if clinically indicated
 
Monitor closely
 
Provide supportive care according to institutional standards
 
When toxicity resolves to Grade 1 or baseline, restart trametinib reduced by one dose level
 
If the Grade 3 toxicity recurs, interrupt trametinib
 
When toxicity resolves to Grade 1 or baseline, restart trametinib reduced by another dose level
 
 |
| Grade 4     | 
 
Interrupt trametinib
 
Monitor closely
 
Provide supportive care according to institutional standards
 
If event resolves to Grade 1 or baseline discuss potential continuation of trametinib with investigator-sponsor; if continuation of treatment agreed then restart trametinib at dose reduced by one dose level
 
If event does not resolve permanently discontinue trametinib
 
       |

**Note:** Approval from the investigator-sponsor is required to restart study treatment after ≥ 28 days of interruption.

Trametinib dose modification guidelines are outlined in Table 5.2 and Table 5.3 for clinically significant toxicities that are deemed related to trametinib (i.e. peripheral and periorbital edema) with the exception of the **following events of special interest**:

- rash (Section 5.2.1)
- diarrhea (Section 5.2.2),
- ejection fraction changes (Section 5.2.3),
- hypertension (Section 5.2.4)
- prolonged QTc (Section 5.2.5)
- pneumonitis (Section 5.2.6),
- visual changes (Section 5.2.7),
- liver chemistry elevation (Section 5.2.8)

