**For these, refer to the relevant sections for dose modification guidelines for adverse events of special interest.**

Treatment or visit delays for public holidays or weather conditions do not constitute a protocol violation.

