**Table 5.5 Management and Dose Modification Guidelines for Rash**

| CTCAE Grade | Adverse Event Management  | Action and Dose Modification  |
|-------------|---|---|
| Grade 1     | 
 
Initiate prophylactic and symptomatic treatment measuresa
 
Use moderate strength topical steroidb
 
Reassess after 2 weeks
 
 | 
 
Continue trametinib
 
If rash does not recover to baseline within 2 weeks despite best supportive care, reduce trametinib by one dose levelc
 
   |
| Grade 2     | 
 
Initiate prophylactic and symptomatic treatment measures
 
Use moderate strength topical steroidb
 
Reassess after 2 weeks
 
             | 
 
Reduce trametinib by one dose level 
 
If rash recovers to ≤grade 1 within 2 weeks, increase dose to previous dose level
 
If no recovery to ≤grade 1 within 2 weeks, interrupt trametinib until recovery to ≤grade 1
 
 
 
Restart trametinib at reduced dose levelc
 
 |
| Grade ≥3    | 
 
Use moderate strength topical steroidsb PLUS oral methyl-prednisolone dose pack
 
Consult dermatologist
 
                                       | 
 
Interrupt trametinib until rash recovers to grade ≤1, after discussion with study PI.
 
Restartc with trametinib reduced by one dose leveld
 
If no recovery to grade ≤2 within 4 weeks, permanently discontinue trametinib
 
   |

Abbreviations: CTCAE = Common Terminology Criteria for Adverse Events

- Rash prophylaxis is recommended for the first 6 weeks of study treatment
- Moderate-strength topical steroids: hydrocortisone 2.5% cream or fluticasone propionate 0.5% cream
- Approval of the investigator-sponsor is required to restart study treatment after >4 weeks of interruption.
- Escalation of study treatment to previous dose level may be considered if no rash is evident 4 weeks after restarting study treatment

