**Table 5.12 Recommended dose modifications for trametinib for retinal pigment epithelial detachments (RPED)a**

| CTCAE Grade   | Action and Dose Modification   |
|---|--|
| Grade 1 RPED (Asymptomatic; clinical or diagnostic observations only)                                   | 
 
• Continue treatment with retinal evaluation monthly until resolution. If RPED worsens follow instructions below
 
   |
| Grade 2-3 RPED (Symptomatic with mild to moderate decrease in visual acuity; limiting instrumental ADL) | 
 
• Interrupt trametinib
 
• Retinal evaluation monthly
 
• If improved to ≤ Grade 1, restart trametinib at lower dose (reduced by 0.5 mg) or discontinue in patients taking trametinib 1 mg daily
 
 |

a. Refers to CTCAE Version 4.03 'Retinopathy'

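### Table 5.11 restarts trametinib at the same dose after a related Grade 2–3 visual event once RPED and RVO are excluded, with no condition that the event has improved

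*Combined protocol and SAP*

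**What the plan says.** Section 5.2.7 sends visual changes and eye-examination findings judged related to treatment to Table 5.11.

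- **Grade 2 and 3.** The ophthalmologist is consulted immediately and trametinib is interrupted. Then: "If RPED and RVO excluded, restart trametinib at same dose level". A diagnosis of RPED leads to the separate RPED table, and RVO to permanent discontinuation.
- **Grade 4.** Consultation, interruption and a serious adverse event report are required. Then: "If RPED and RVO excluded, may consider restarting trametinib at same or reduced dose after discussion with study medical monitor". RPED or RVO at this grade means permanent discontinuation.

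The general rule is in Table 5.3. After an interruption for a Grade 2 or 3 event it says "When toxicity resolves to Grade 1 or baseline, restart trametinib", at the current dose for Grade 2 and one level lower for Grade 3. For Grade 4 it says "If event resolves to Grade 1 or baseline discuss potential continuation of trametinib with investigator-sponsor", and if the event does not resolve the drug is stopped for good.

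Visual changes are one of eight events of special interest excepted from Tables 5.2 and 5.3. For these the reader is told to "refer to the relevant sections for dose modification guidelines for adverse events of special interest".

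**The concern.** The only condition for restart in the Grade 2–3 row is a negative diagnosis. Excluding RPED and RVO does not show that the event has gone, or that the drug did not cause it, since the table covers events already considered related. Section 4.1.1 lists other trametinib eye reactions: blurred vision and visual impairment as common, uveitis, papilledema and retinal detachment as uncommon. A site that follows the row literally would resume the same dose while a related Grade 3 eye event of another kind was still active. RPED of the same grade would have to improve first and would return at a lower dose.

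At stake are patient safety and consistency between sites, since each would have to supply its own threshold.

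**Working it through.** The plan states no figure to reproduce. The check is whether any other text supplies a recovery condition, and whether visual events are alone in lacking one.

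**Step 1. Restart conditions after a hold, for the eight events of special interest**

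| Event (table) | Needed before restart | Most severe category |
|---|---|---|
| Rash (5.5) | Grade 1 or lower | Grade 3 and above: "Interrupt trametinib until rash recovers to grade ≤1" |
| Diarrhea (5.6) | Grade 1 or lower | Grade 3–4 or complicated: same condition |
| LVEF (5.7) | At or above the lower limit of normal, and an absolute fall of at most 10% from baseline | Symptomatic Grade 3–4: permanent stop |
| Hypertension (5.8) | Blood pressure well controlled | Refractory or crisis: permanent stop |
| QTc (5.9) | Grade 1 or baseline | Same condition; permanent stop on recurrence |
| Pneumonitis (5.10) | Grade 1 or lower | Grade 4: permanent stop |
| Liver chemistry (5.13) | Grade 1 or lower | Grade 4: off protocol therapy |
| Visual, neither RPED nor RVO (5.11) | None | Grade 4: none, but restart is discretionary |

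Seven of eight have a recovery or control condition, and none of those seven allows restart without one, even in its most severe category. Table 5.14 is stricter still on pneumonitis, which does not change the count. Within visual changes, Grade 2–3 RPED is covered: Table 5.12 requires improvement to Grade 1 or lower.

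**Step 2. Does other text fill the gap?**

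- Table 5.3: no. Visual changes are excepted from it.
- The note under Table 5.3 on sponsor approval after 28 or more days of interruption: it depends on time, not on recovery.
- Section 5.3 (clinician judgment, dose delay, possible dose reduction): it permits caution and sets no threshold.
- Section 7.5 (re-challenge only if safe and ethical): the same.
- Sections 3.4 and 6.1.6 (stopping and withdrawal): they end treatment; they do not govern restart.

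**Step 3. How many patients?** For one reaction term the expected number is 27 × p × f. Here p is the all-grade related frequency in Section 4.1.1 (melanoma, n = 329, assumed to carry over to lung cancer). The share f counts events that are Grade 2–4, fall under Table 5.11 and are unresolved when RPED and RVO are excluded. The documents do not give f, so its range is 0 to 1. Setting f = 1 gives only a ceiling:

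- Common term (1% to <10%): 27 × 0.01 = 0.27 to 27 × 0.10 = 2.7 (not reached).
- Uncommon term (0.1% to <1%): 27 × 0.001 = 0.027 to 27 × 0.01 = 0.27 (not reached).

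With f unknown, the affected number per term lies anywhere from 0 to below these upper ends.

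**The case against.** **The hold is diagnostic by design.** The Grade 1 row shows this: if a fundus examination cannot be done within 7 days, the drug is held until the two retinal diagnoses are excluded. Ending a diagnostic hold when the diagnosis is excluded is coherent. This explains the hold, but it leaves open what to do about a related Grade 2–3 event that persists.

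**Table 5.3 is not uniformly stricter.** It interrupts Grade 2 and 3 events only if clinically indicated, so the general rule tolerates dosing through an unresolved related Grade 3 event. Table 5.11 makes both the hold and the specialist consultation mandatory. This stands, and it narrows the point. Treatment during an unresolved event is not peculiar to eye events; restart after a hold with no recovery condition is.

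**Recovery to Grade 1 is not universal.** Held Grade 3 fatigue may resume at Grade 2 or lower (Table 5.14). True, but that is still a threshold.

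**RPED is an imperfect comparator.** It is one of the diagnoses the hold exists to find, and Table 5.12 is headed as a recommendation. Fair; the comparison with the other seven events carries more weight.

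**Scope is uncertain.** Footnote a of Table 5.11 ties its grading to one residual CTCAE eye term, so some listed reactions might be graded elsewhere. The section text, the table title and the list of exceptions all point to visual changes generally. On either reading, the events inside the table lack a recovery condition.

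**Grade 4.** A reader might infer that the Grade 4 row is as open as the Grade 2–3 row. The documents do not support that: restart there is only something to consider, a reduced dose is allowed, and the medical monitor must be involved.

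**Conclusion.** The gap is real in the Grade 2–3 row, which is worded as an instruction and is out of line with the protocol's other seven events of special interest. It is present but weaker in the Grade 4 row. It merits an amendment on safety grounds. It has no bearing on the sample size or the response-rate test.

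Two stronger readings are tempting and should be resisted.

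- A reader might infer that the protocol compels same-dose re-exposure in an active eye event. It does not: the general provisions on judgment and re-challenge allow a longer hold or a lower dose. They set no recovery threshold, so practice can differ between sites.
- A reader might turn the common frequency band into a chance of at least one affected patient, from 1 − 0.99^27 = 24% to below 1 − 0.90^27 = 94%. Those figures describe any related event of that term, at any grade, in melanoma. They do not measure Grade 2–4 events still unresolved at restart.

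That few of the 27 patients would be affected is therefore a judgment, not an estimate. The conclusion assumes that Table 5.11 governs related visual changes generally.

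**What to change.** Amend two rows of Table 5.11.

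- **Grade 2–3:** after "If RPED and RVO excluded, restart trametinib at same dose level" add *once the event has resolved to Grade 1 or lower or to baseline; if it has not resolved, restart only with the agreement of the ophthalmologist and the medical monitor*.
- **Grade 4:** to the existing condition that RPED and RVO are excluded, add *and the event has resolved to Grade 1 or lower or to baseline*. Leave the rest of the row as it is.

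The threshold is the protocol's own, from Table 5.3. The exception in the Grade 2–3 row is deliberate: without it, an event that never returned to Grade 1 or baseline would bar a patient with advanced cancer from treatment indefinitely. At Grade 4 a firm bar matches Table 5.3. Whether a Grade 3 event should also return at a lower dose is left to the medical team.

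The cost is a longer interruption for a few patients and possibly a repeat eye assessment. The required consultation comes at onset, and Section 5.3 schedules examinations only at baseline, month 1, month 6 and then annually, so documenting resolution may need an extra visit.

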**Table 5.12 Recommended dose modifications for trametinib for retinal pigment epithelial detachments (RPED)a**

| CTCAE Grade   | Action and Dose Modification   |
|---|--|
| Grade 1 RPED (Asymptomatic; clinical or diagnostic observations only)                                   | 
 
• Continue treatment with retinal evaluation monthly until resolution. If RPED worsens follow instructions below
 
   |
| Grade 2-3 RPED (Symptomatic with mild to moderate decrease in visual acuity; limiting instrumental ADL) | 
 
• Interrupt trametinib
 
• Retinal evaluation monthly
 
• If improved to ≤ Grade 1, restart trametinib at lower dose (reduced by 0.5 mg) or discontinue in patients taking trametinib 1 mg daily
 
 |

a. Refers to CTCAE Version 4.03 'Retinopathy'

### 5.2.8 Guidelines for Liver Chemistry Elevation

**Table 5.13**

| Grade of Event | Management/Next Dose for Trametinib                                     |
|----------------|---|
| ≤ Grade 1      | No change in dose   |
| Grade 2        | Hold until ≤ Grade 1
Resume at same dose level                       |
| Grade 3        | Hold* until ≤ Grade 1
Resume at one dose level lower, if indicated** |
| Grade 4        | Off protocol therapy  |

### 5.2.9 Guidelines for other toxicity

**Table 5.14**

| Worst toxicity (CTCAE 4.03 Grade)*  | Dose Modifications for trametinib  |
|--|---|
| GENERAL DISORDERS   |   |
| Fatigue (asthenia)  |   |
| Grade 1 or 2   | Maintain dose level   |
| Grade 3  | If grade 3 fatigue resolves to Grade 2 in ≤ 7 days, maintain dose level
If grade 3 fatigue lasts > 7 days, omit dose until resolved to ≤ Grade 2 and then ↓ dose level   |
| PULMONARY   |   |
| Notes:   |   |
| 
 
• Withhold trametinib for acute onset of new or progressive unexplained pulmonary symptoms, such as dyspnea, cough and fever and during diagnostic workup for pneumonitis/ILD.
 
• During evaluation of potential grade 2, 3, and 4 pneumonitis, if an infectious etiology is confirmed (i.e., pneumonia) and pneumonitis is excluded, then consider resuming at current dose level after the pneumonia resolves.
 
 |   |
| PNEUMONITIS   |   |
| Worst toxicity (CTCAE 4.03 Grade)*  | Dose Modifications for trametinib  |
| Any Grade treatment-related ILD/pneumonitis  | Permanently discontinue patient from study.   |
| CARDIAC INVESTIGATIONS  |   |
| Electrocardiogram QT corrected (QTc) interval prolonged   |   |
| Grade 1 (QTc 450-480 ms)
Grade 2 (QTc 481-500 ms)   | Maintain dose level   |
| Grade 3 (QTc ≥ 501 ms on at least two separate ECGs)   | Omit dose until QTC is less than 481 ms, then ↓ dose level
Perform an analysis of serum potassium, and if below lower limit of normal, correct with supplements to within normal limits.
-Repeat ECG in 24 hours, or less, as clinically indicated; continue monitoring as clinically indicated until QTc < 481 ms
-Repeat ECGs 7 days after dose resumption for all patients who had therapy interrupted due to QTc ≥ 501 ms. |
| Grade 4 (QTc ≥ 501 or > 60ms change from baseline and Torsades de pointes or polymorphic ventricular tachycardia or signs/symptoms of serious arrhythmia)  | Permanently discontinue patient from trametinib.  |

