**Table 5.2 Dose Modifications and Dosing Delays**

| Dose Level | Dose of Study Drug |
|------------|--------------------|
| -2         | 1 mg daily         |
| -1         | 1.5 mg daily       |
| 1          | 2 mg daily         |

Dose adjustment for trametinib below 1 mg QD is not recommended.

A maximum of two trametinib dose level reductions are allowed. If a third dose level reduction is required, treatment will be permanently discontinued.

If a dose reduction of trametinib is required, but the toxicity resolves and no additional toxicities are seen after two cycles of treatment, the dose of trametinib may be re-escalated but should not exceed 2 mg once daily.

The following dose modification rules will be used with respect to potential toxicity. Toxicity will be assessed according to the NCI Common Terminology Criteria for Adverse Events [Version 4.03 \(CTCAE v4.03\)](#).

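### Tables 5.10 and 5.14 give conflicting instructions for treatment-related pneumonitis, Tables 5.9 and 5.14 do so for QTc prolongation, and the visible text does not say which prevails

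*Combined protocol and SAP*

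**What the plan says.** After Table 5.3, Section 5.2 lists events of special interest that fall outside Tables 5.2 and 5.3. Pneumonitis is sent to Section 5.2.6 and prolonged QTc to Section 5.2.5. Section 5.3 repeats both pointers. Neither list mentions Section 5.2.9.

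**Pneumonitis, Table 5.10 (Section 5.2.6).**
- Grade 1: "Continue trametinib at current dose".
- Grades 2 and 3: "Interrupt trametinib until recovery to grade ≤1".
- Grade 2 after recovery: "Restart with trametinib reduced by one dose level".
- Grade 3 after recovery: "After consultation with medical monitor, study treatment may be restarted reduced by one dose level".
- Grades 2 and 3 without recovery: "If no recovery to grade ≤1 within 4 weeks, permanently discontinue study treatment".
- Grade 4: permanent stop.

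**Pneumonitis, Table 5.14 (Section 5.2.9).** For "Any Grade treatment-related ILD/pneumonitis" the action is "Permanently discontinue patient from study". A note in the same table withholds the drug while pneumonitis or ILD is being worked up.

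**QTc.** Table 5.9 and Table 5.14 each give a trigger, a restart rule and stopping criteria. They are compared below.

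**Dose ladder, Table 5.2.** The levels are 2, 1.5 and 1 mg, with at most two reductions: "If a third dose level reduction is required, treatment will be permanently discontinued".

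**The concern.** A clinician with a patient who has confirmed treatment-related pneumonitis can find two rules in the same section of the protocol. One keeps the patient on trametinib or allows a restart. The other ends treatment for good.

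The main stake is patient safety. In a multicenter trial, one site could continue the drug and another stop it for the same event at the same grade, with neither deviating from the protocol. One mistake leaves a patient exposed to a drug that may be injuring the lung. The other takes away treatment from a patient who may be benefiting.

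The safety results are also touched. Section 2.4.2 lists events leading to discontinuation, and events leading to interruption, reduction or delay, as secondary safety endpoints. Their counts would depend partly on which table each site used.

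**Working it through.** The plan gives no figure to reproduce. The check sets the tables side by side and follows the dose through Table 5.2.

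**Step 1: do the tables cover the same patients?** Section 5.2 introduces its guidance for toxicities judged related to trametinib, and the Table 5.14 row is for treatment-related events. Treatment-related pneumonitis therefore falls under both tables, and relatedness does not separate them.

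**Step 2: pneumonitis, treatment-related.**

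| Event | Table 5.10 | Table 5.14 | Result |
|---|---|---|---|
| Grade 1 | same dose | permanent stop | conflict at every dose |
| Grade 2, recovered within 4 weeks | restart one level lower | permanent stop | conflict at 2 and 1.5 mg |
| Grade 3, recovered within 4 weeks | restart one level lower permitted after medical monitor consultation | permanent stop | conflict at 2 and 1.5 mg |
| Grade 2 or 3, not recovered | permanent stop | permanent stop | agree |
| Grade 4 | permanent stop | permanent stop | agree |

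One level is 0.5 mg. From 2 mg the Table 5.10 restart is 2 − 0.5 = 1.5 mg; from 1.5 mg it is 1.5 − 0.5 = 1 mg. A patient at 1 mg has used both reductions. A further one would be the third, which Table 5.2 turns into a permanent stop, so for recovered Grades 2 and 3 both tables then stop the drug. Table 5.12 uses the same logic for retinal detachment at 1 mg.

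**Step 3: during the work-up.** For Grade 1, Table 5.10 calls for evaluation for infection and recommends CT while the drug continues. The Table 5.14 note holds the drug during a pneumonitis or ILD work-up. These also disagree.

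**Step 4: QTc.**

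| Situation | Table 5.9 | Table 5.14 |
|---|---|---|
| Trigger | QTcB of 501 msec or more, averaged over triplicate ECGs; uncorrected QT above 600; separate 530 msec limit with bundle branch block | 501 msec or more on two or more separate ECGs; no bundle branch block limit |
| First event | restart at the same dose if the medical monitor agrees | restart at a lower level |
| Recurrence | permanent stop | omit and reduce again |
| 501 msec or more with torsades or serious arrhythmia | no exception to the restart rule | permanent stop |
| Repeat ECGs | no schedule | within 24 hours, and 7 days after resumption |

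Reading the Table 5.14 reduction as one level, the first-event restart dose is 2 v 1.5 mg, or 1.5 v 1 mg. At 1 mg it becomes restart v stop. For recurrence, take a patient who starts at 2 mg and has no other reductions. Table 5.14 gives 1.5 mg after the first event and 1 mg after the second; Table 5.9 stops at the second.

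The thresholds for resuming are compatible: Grade 1 or baseline in one table, below 481 msec in the other.

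**Step 5: is there a rule of precedence?** Section 5.3 says that dose follows the system with the worst toxicity. That chooses between organ systems, not between two tables for one event at one grade. No other visible sentence ranks the tables.

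**The case against.** The best counter-argument is the routing. Two separate lists send pneumonitis to Section 5.2.6 and QTc to Section 5.2.5 by number, and Section 5.2.9 is headed as covering other toxicity. A site could reasonably take Tables 5.10 and 5.9 as governing and the Table 5.14 rows as leftovers. This stands as a sensible default, and the fix below uses it. It does not settle the matter. The Section 5.2 exception is made from Tables 5.2 and 5.3 only, Section 5.2.9 is itself part of Section 5.2, and its rows name the same events. Ignoring those rows would also discard the arrhythmia stop and the repeat-ECG schedule, which appear nowhere else.

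The Table 5.14 header carries an asterisk with no visible footnote. A lost note could bear on scope, so the finding is limited to the visible text.

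There are real safeguards. Grade 2 restart follows CT, infection work-up, a pulmonologist consultation and recovery. Grade 3 and QTc restarts involve the medical monitor. Restart after 28 days or more of interruption needs investigator-sponsor approval (Table 5.3 note). Appendix 4 provides for continuous review by the Study Chair, monthly Site Committee discussion of each patient and monthly site calls. These may catch divergent handling. They do not say which rule applies, and Table 5.10 asks for no medical monitor contact at Grade 1.

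The objection that QTc is the lesser issue is accepted.

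**Conclusion.** The inconsistency is real and should be corrected. For treatment-related pneumonitis the instructions are opposed at Grade 1 at every dose, and at recovered Grades 2 and 3 at 2 mg and 1.5 mg. The QTc conflicts are secondary.

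Three stronger inferences are not supported:
- **That the response rate or its test is affected.** The only pneumonitis frequency is from 329 melanoma patients (1% to under 10%, Section 4.1.1). This trial excludes prior ILD or pneumonitis. Nothing gives the timing of pneumonitis relative to response. Neither the number of patients affected nor any shift in ORR can be derived.
- **That a count of conflicting rows measures the problem.** Any count depends on how rules found in only one table are classed, so none is offered.
- **That one pneumonitis rule is clinically wrong.** The documents do not show whether the any-grade stop or the graded approach was intended.

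Assumptions: removal from study in Table 5.14 includes stopping trametinib; a patient at 1 mg has had two reductions that were not reversed. Table 5.2 does not say how a reduction followed by re-escalation is counted.

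**What to change.** State one rule per event.

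- **Pneumonitis.** The default that fits the protocol's own routing is Table 5.10, extended to name ILD. If the investigator-sponsor and medical monitor decide that the any-grade stop was intended, change Table 5.10 to match.
- **QTc.** The default is Table 5.9, with one ECG trigger and its recurrence stop kept. Move into it the Table 5.14 permanent stop for torsades, polymorphic ventricular tachycardia or serious arrhythmia, including the limb for a change of more than 60 ms from baseline, which Table 5.9's triggers can miss. Also move the 24-hour and 7-day repeat ECGs.
- **Work-up.** State in Section 5.2.6 whether trametinib is held or continued while suspected Grade 1 pneumonitis is investigated, so that the withholding note and the Grade 1 row agree.
- **Table 5.14.** Replace its pneumonitis and QTc rows with cross-references to Sections 5.2.6 and 5.2.5.
- **Sites.** Notify all of them.

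The cost is amendment wording and a site notice. No new procedures or patients are needed.
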